4.3.2 Criteria for Ad Hoc Data Safety Monitoring Board Review of Study

In the event that any of the following criteria are encountered, the DSMB may, as described in the DSMB Charter, convene to review available data and make recommendations, including but not limited to, if the cohort should stop or if it is necessary to pause the study, enrollment, or treatment and/or make recommendations to modify the Protocol (ie, decrease or change the dose of study drug, modify safety monitoring):

- If any unacceptable toxicity (as determined by the Investigator or Sponsor's Medical Monitor) occurs;
- If ≥ 1 SAE considered attributable to AP-PA02 (confirmed by unblinding) occurs; or
- If ≥ 2 of all treated subjects experience similar SAEs or Grade 3 (CTCAE version 5.0) considered attributable to AP-PA02 (confirmed by unblinding).

Note: All \geq Grade 3 (CTCAE version 5.0) laboratory abnormalities should be confirmed with a repeat test within 24 hours.

If the DSMB recommends, and the Sponsor then implements, stopping study treatment and, subsequently, the Sponsor, independent of or following a DSMB recommendation, proposes to restart the study, a substantial amendment will be submitted to regulatory agencies and Institutional Review Boards (IRBs)/Independent Ethics Committees (IECs). The study will not restart until the amendment has been approved by regulatory agencies and IRBs/IECs. These requirements are not applicable if the Sponsor pre-emptively pauses study treatment for subject safety pending DSMB review and the DSMB recommends resuming study treatments and/or any study modifications recommended do not represent substantial Protocol changes.

4.4 Withdrawal or Modification of Individual Subject Study Participation

Participation of a subject in this clinical study will be discontinued for any of the following reasons:

- The subject or legally authorized representative withdraws consent or requests discontinuation from the study for any reason;
- The subject becomes pregnant; or
- The subject has not demonstrated to clinic staff that he/she can properly administer study drug, the subject has no appropriate caregiver who has demonstrated that he/she can properly administer study drug to the subject, or the subject is not able or willing to return to the clinic for study drug administration to ensure that the subject properly receives study drug as per the Protocol.

The Investigator may, with concurrence of the Medical Monitor or Sponsor, discontinue or modify a subject's study participation for any of the following reasons:

- Occurrence of any AE (whether or not attributed to study treatment), medical condition, or circumstance that does not allow the subject to adhere to the requirements of the Protocol or continued participation is not in the best interest of the subject; or
- Subject failure to comply with Protocol requirements or study-related procedures.

Subjects will be considered lost to follow-up if, after completing study treatment, they fail to attend a required visit or are unresponsive despite 3 attempts to reach them by telephone, text message,

email, and/or regular postal mail. Such subjects may, with the concurrence of the Sponsor, be terminated from study participation and notification sent by registered mail to the last known address. These contact attempts will be documented in both the study record and the subject's medical record.

Subjects who discontinue prematurely from the study or whose participation is modified will be strongly encouraged to complete the full panel of safety assessments scheduled for the ET Visit. The reason for subject withdrawal must be documented in the eCRF.

Withdrawn or lost to follow-up subjects may be replaced to ensure adequate numbers of evaluable subjects at the discretion of the Sponsor. Subjects who discontinue for study drug-related safety or tolerability reasons will not be replaced.

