4.3.1 Criteria for Potential Interruption or Discontinuation of Study Drug in Individual Subjects

In the event that any of the following criteria are encountered, the Investigator will review the AE with the Medical Monitor as soon as feasible. The Investigator will hold the next administration pending that review. The Investigator and Medical Monitor in consultation with the Sponsor will decide whether to continue to hold study treatment pending additional information or to discontinue study treatment.

- \geq Grade 3 AE or laboratory abnormality per Common Terminology Criteria for AEs (CTCAE) version 5.0 considered attributable to AP-PA02 (confirmed by unblinding). If the event or laboratory test is not listed in the CTCAE, the event or laboratory test should be graded by applying the CTCAE guidelines detailed in [Section 8.1.3](#);

Note: Clinically significant laboratory abnormalities classified per above should be confirmed with a repeat test within 24 hours.

- Any serious AE (SAE) considered attributable to AP-PA02 (confirmed by unblinding); or
- Acute bronchospasm, defined as a decrease in absolute FEV₁ of \geq 15% accompanied by symptoms requiring medical intervention, occurring from the Baseline value up to 4 hours following study drug administration and persisting following administration of a short-acting bronchodilator.

Any subject who prematurely discontinues from study drug, will have documented the reason and date of discontinuation in the electronic case report form (eCRF) and the subject should be encouraged to continue to complete all safety and key efficacy assessments at subsequent study visits. For subjects who do not agree to participate in subsequent study visits, study staff should make every effort to complete the full panel of assessments scheduled for the Early Termination (ET) Visit.

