5.5.3 Study Drug Administration

The AP-PA02 dose will be administered to each subject as 2 fractionated doses per treatment day. The dosages shown below are estimated (approximate) PFU:

- Each fractionated dose: 1.5×10^{11} PFU;
- Total dose per treatment day: 3×10^{11} PFU; and
- Total dose per 10-day treatment course: 3×10^{12} PFU.

AP-PA02 will be administered in the clinic [REDACTED] during Visit 1/Day 1 (both doses), Visit 2/Day 5 (morning dose only), and Visit 3/Day 10 (morning dose only). Subjects will administer AP-PA02 at home on all other treatment days.

The placebo will be administered in the clinic/at home using the same fractionated dosing schedule and duration as AP-PA02 and [REDACTED]. The placebo will be administered in the clinic during Visit 1/Day 1 (both doses), Visit 2/Day 5 (morning dose only), and Visit 3/Day 10 (morning dose only). Subjects will administer placebo at home on all other treatment days.

On Visit 1/Day 1, clinic staff will administer the first dose of AP-PA02 or placebo. The subject and/or caregiver will administer the second dose of AP-PA02 or placebo with clinic staff observation after the subject has been trained on proper administration. Clinic staff will confirm

the subject/caregiver is comfortable with administering AP-PA02 or placebo during this visit. If the subject is not comfortable administering AP-PA02 or placebo, the subject may visit the clinic for study drug administration until he/she or the caregiver is comfortable with proper study drug administration.

Subjects in Cohort A will receive study treatment (AP-PA02 or placebo) administered as 1 dose distributed over 2 administrations given 6 hours apart on the same day on Day 1 and 10-12 hours apart each day on the remaining days on 10 consecutive days, with 28 days of follow-up after the last study drug dose. Subjects in Cohort B will receive study treatment (AP-PA02 or placebo) administered as 1 dose distributed over 2 administrations given 6 hours apart on the same day on Day 1 and 10-12 hours apart each day on the remaining days for 10 consecutive days plus their current antipseudomonal inhaled antibiotic for 28 days (10 days of study drug treatment plus an additional 18 days). Subjects in Cohort B will also have 28 days of follow-up after the last study drug dose.

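### Protocol 4.4 ends study participation for a pure dosing problem while 4.3.1 would keep the subject for key efficacy visits, so a Day 17 culture could go uncollected from a willing subject

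*Protocol*

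**What the plan says.** Protocol 4.4 has two lists. The first is mandatory: "Participation of a subject in this clinical study will be discontinued for any of the following reasons". It has three entries: withdrawal of consent, pregnancy, and failure of drug administration. The third covers a subject who has not shown that they can administer the drug, who has no caregiver able to do so, or where "the subject is not able or willing to return to the clinic for study drug administration". The second list is discretionary. With Medical Monitor or Sponsor agreement, the Investigator may "discontinue or modify a subject's study participation for any of the following reasons", namely adverse events or circumstances that prevent adherence, and non-compliance.

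For both lists, 4.4 then says: "Subjects who discontinue prematurely from the study or whose participation is modified will be strongly encouraged to complete the full panel of safety assessments", meaning those of the ET Visit. It also allows replacement: "Withdrawn or lost to follow-up subjects may be replaced to ensure adequate numbers of evaluable subjects at the discretion of the Sponsor", with one exception: "Subjects who discontinue for study drug-related safety or tolerability reasons will not be replaced".

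Protocol 4.3.1 covers any subject who stops study drug early, whatever the reason: "the subject should be encouraged to continue to complete all safety and key efficacy assessments at subsequent study visits". The full ET panel is its fallback for those who decline later visits.

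Protocol 5.5.3 offers a temporary alternative to home dosing: "the subject may visit the clinic for study drug administration until he/she or the caregiver is comfortable with proper study drug administration".

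The primary endpoint is *P. aeruginosa* density in induced sputum at Visit 5/Day 17 (SAP 5.1 and 9.1). SAP 7.3 does not impute missing endpoints. SAP 7.4 derives no visit windows and tabulates by nominal visit.

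**The concern.** The third mandatory ground is about getting the drug into the subject. It says nothing about whether the subject would attend follow-up. Even so, it ends participation altogether, alongside consent withdrawal and pregnancy, where ending participation follows from the subject's own choice or from Protocol 8.4.

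Such a subject has also stopped study drug, so 4.3.1 applies too and points the other way on later efficacy visits. The wording of 4.4 is mandatory and that of 4.3.1 is encouragement, so a site could reasonably follow 4.4. A randomized, dosed subject who would have given a Day 17 sample then has no primary value. Replacement can restore the count but not that subject's outcome.

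**Working it through.** **The rules side by side, for a subject whose drug cannot be administered**

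| Question | Protocol 4.3.1 | Protocol 4.4, third mandatory ground |
|---|---|---|
| Trigger | Study drug stopped, any reason | Drug cannot be properly given and clinic dosing is not possible or not accepted |
| Status | Stays in the study | Participation ends |
| Later visits | Safety and key efficacy encouraged | None requested |
| ET Visit | Full panel, only if later visits are declined | Safety assessments encouraged |
| Day 17 culture | Sought | Not sought |

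The 4.4 entry is loosely punctuated. Read with 5.5.3, its sensible meaning is that self-administration, caregiver administration and clinic dosing have all failed. The table uses that narrow reading, and the overlap remains.

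**Can an ET culture stand in?** The note to Table 1 in Appendix A asks for the full ET panel, and the ET column includes induced sputum and culture. A sample may therefore exist. However, SAP 7.4 keeps nominal visits and SAP 7.3 does not impute, so nothing assigns that sample to Visit 5.

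**Could someone decline clinic dosing but attend Day 17?** Counts from Protocol 5.5.2 and 5.5.3:
- Total administrations: 10 days × 2 = 20.
- In clinic: Day 1 both, Day 5 morning, Day 10 morning = 4.
- At home: Days 2–4 (6) + Day 5 second (1) + Days 6–9 (8) + Day 10 second (1) = 16.

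Moving all home dosing to the clinic would mean up to 16 further clinic administrations. This is an upper bound: 2 of the 16 fall on days when the subject already attends, and 5.5.3 intends clinic dosing to be temporary. Visit 5 is one visit. Refusing the former does not imply refusing the latter.

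**Scale of one lost value.** The plan has no power calculation or dropout rate to reproduce. Inputs are 24 per cohort at 2:1, so 16:8, and a 95% interval from a two-sample t test for each cohort separately (SAP 9.1). Half-width in SD units = t(0.975, n1+n2−2) × √(1/n1 + 1/n2).
- 16:8: 2.074 × √(1/16 + 1/8) = 0.898
- 15:8 (one AP-PA02 value lost): 2.080 × √(1/15 + 1/8) = 0.910, +1.4%
- 16:7 (one placebo value lost): 2.080 × √(1/16 + 1/7) = 0.942, +4.9%

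SAP section 6 also drops AP-PA02 subjects enrolled before the first DSMB meeting, without giving a number, so the analysed AP-PA02 arm may be smaller than 16.

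**The case against.** The strongest reply is that 4.3.1 governs stopping drug and 4.4 governs leaving the study, and that different follow-up for different events is normal. That is right in general. The two sections collide only in this one ground, where a dosing problem is treated as leaving the study.

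The case should also be rare. Inclusion criterion 12 asks for experience or comfort with inhaled antibiotics, or a caregiver's comfort. Criterion 14 asks for ability to comply with visits and procedures. Day 1 includes training and an observed second dose, and clinic dosing is available. All of this stands, and it limits the importance of the point.

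A recovered value might also go unused. A subject stopped on Day 1 may have had only 1 or 2 of 20 administrations, and SAP 6.2 excludes major violations that could affect the validity of the primary evaluation. This stands too. But that decision is made at blinded review, and a culture that was never collected cannot be considered there. SAP section 9 otherwise analyses efficacy by randomized group.

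Three stronger readings might be inferred, and the documents do not support them:
- *That 4.4 ends follow-up for adverse events and non-compliance generally.* Those grounds are discretionary and already allow participation to be modified, and 4.3.1 still covers a subject who only stops drug. Non-compliance can also mean refusing the visits themselves.
- *That the primary comparison is biased.* Inability to use the nebulizer would usually show on Day 1, under blinding, with the same dosing schedule in both arms. Nothing shows that such losses relate to treatment.
- *That the Protocol as a whole asks only for ET safety assessments.* Both the Table 1 note and 4.3.1 ask for the full ET panel. Protocol 5.4 mentions only safety assessments after unblinding but does not displace 4.3.1.

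**Conclusion.** The overlap is real and confined to the third mandatory ground of Protocol 4.4. For that ground, one rule ends participation, another keeps the subject for key efficacy assessments, and no precedence is stated. Under 4.4 a willing subject's primary culture would not be collected, and the SAP provides no substitute.

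The importance is minor. The number of subjects affected cannot be estimated from the documents and should be very small, and no size or direction of bias can be shown. The 1.4% and 4.9% figures describe losing any one unreplaced value for any reason, from an assumed full 16:8 cohort. They do not measure this defect. Replacement is open for this ground unless the stop is a drug-related safety or tolerability one. It would restore the interval width but not the missing outcome.

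The conclusion assumes that a site would follow the mandatory wording of 4.4 and that the subject would still attend Day 17. Both are plausible; neither is certain.

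**What to change.** Move the drug-administration ground in Protocol 4.4 from the reasons for ending participation to the reasons for stopping study drug. Add to 4.4 that subjects who stop study drug without withdrawing consent follow 4.3.1 and, at minimum, are asked to attend Visit 5/Day 17 with induced sputum, unless the Investigator judges that unsafe.

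Leave the consent-withdrawal and pregnancy grounds as they are, along with the discretionary adverse-event and non-compliance grounds. Aligning the ET wording in 4.4 or the wording in 5.4 would be tidying only; the ET change would recover no Day 17 data.

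The cost is wording, with no new visits or procedures. A few subjects off drug would be asked to attend visits and undergo sputum induction, and SAP 6.2 may still exclude some of their values. Protocol 12.1 puts every amendment through the same review and approval as the original Protocol, and the study plans approximately 30 sites, so this should go into the next amendment and not prompt one of its own.

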4.4.1 Termination of the Study

The Sponsor may terminate the study at any time and for any reason, including, but not limited to, recommendation by the DSMB, new nonclinical information regarding the study treatment, or if required by regulatory authorities.

[figure not shown]
Depending on the circumstances, termination procedures may or may not include completion of study treatment as assigned for all subjects who have received at least 1 dose. After a subject receives their last treatment, all EOS treatment safety evaluations will be completed.

5 STUDY TREATMENTS

5.1 Treatment Groups

Cohort A subjects will receive AP-PA02 or placebo. Cohort B subjects will receive AP-PA02 plus their current antipseudomonal inhaled antibiotic or placebo plus their current antipseudomonal inhaled antibiotic. See [Figure 1](#) for the enrollment schematic.

5.2 Rationale for Dosing

5.3 Randomization and Blinding

A total of 24 eligible subjects will be randomized to Cohort A to receive either AP-PA02 or placebo (2:1 ratio) administered via inhalation. A total of 24 eligible subjects will be randomized to Cohort B to receive either AP-PA02 plus their current antipseudomonal inhaled antibiotic or placebo plus their current antipseudomonal inhaled antibiotic (2:1 ratio) administered via

inhalation. Up to an additional 2 optional cohorts (up to 30 subjects in each cohort) may be included to evaluate different doses and durations of treatment after DSMB review.

This is a double-blind study. All subjects, Investigators, and study and Sponsor personnel involved in the conduct of the study will be blinded to subject treatment assignment. There will be a designated unblinded statistician who will generate and have access to the randomization code. The unblinded statistician and other personnel who may become unblinded will not otherwise participate in any study procedures.

5.4 Breaking the Blind

Unblinding at the request of the Investigator should occur only in the event of a severe AE or SAE that is reasonably assessed as treatment related and for which it is necessary to know the treatment assignment to determine an appropriate course of therapy for the subject. If the Investigator must identify the treatment assignment of an individual subject, the Investigator or qualified designee should request the treatment assignment from the centralized randomization system. They should not attempt to get this information from the site's unblinded study team. The Investigator is advised to not reveal the treatment assignment to any other site, Sponsor, or Contract Research Organization personnel.

Whenever possible, prior to proceeding with unblinding, the Investigator will contact the Sponsor to discuss the need to break the blind. The Investigator will notify the Sponsor as soon as is practical in the event of the study blind being broken and will document the reason. In the event this is not possible, the Investigator should contact the Sponsor as soon as possible to discuss the event without revealing the treatment assignment. The Investigator must document the subject identification, the date and time of breaking the blind, and must clearly explain the reasons for breaking the blind.

Medically necessary care should not be delayed for unblinding information (ie, the Investigator should treat the subject based on the subject's signs/symptoms without waiting for the unblinding process to be completed).

Subjects who are unblinded and discontinue study drug should continue to complete all safety assessments at subsequent study visits.

5.5 Drug Supplies

5.5.1 Formulation and Packaging

[REDACTED]

[REDACTED]

5.5.2 Study Drug Preparation and Dispensing

[REDACTED]

[REDACTED]

[REDACTED]

[REDACTED]

[REDACTED]

[REDACTED]

Study drug will be administered in the clinic by qualified site personnel/at home by the subject via the designated study nebulizer, until all study drug solution has been administered. [REDACTED]

[REDACTED] The subject and/or subject's caregiver will be trained on administration of study drug for administration at home. The subject will receive study drug doses for home administration on Visit 1/Day 1 for treatment Days 2 through 4 and on Visit 2/Day 5 for treatment Days 5 (second dose) through 9, and on Visit 3/Day 10 for treatment Day 10 (second dose).

[REDACTED]

5.5.3 Study Drug Administration

The AP-PA02 dose will be administered to each subject as 2 fractionated doses per treatment day. The dosages shown below are estimated (approximate) PFU:

- Each fractionated dose: 1.5×10^{11} PFU;
- Total dose per treatment day: 3×10^{11} PFU; and
- Total dose per 10-day treatment course: 3×10^{12} PFU.

AP-PA02 will be administered in the clinic [REDACTED] during Visit 1/Day 1 (both doses), Visit 2/Day 5 (morning dose only), and Visit 3/Day 10 (morning dose only). Subjects will administer AP-PA02 at home on all other treatment days.

The placebo will be administered in the clinic/at home using the same fractionated dosing schedule and duration as AP-PA02 and [REDACTED]. The placebo will be administered in the clinic during Visit 1/Day 1 (both doses), Visit 2/Day 5 (morning dose only), and Visit 3/Day 10 (morning dose only). Subjects will administer placebo at home on all other treatment days.

On Visit 1/Day 1, clinic staff will administer the first dose of AP-PA02 or placebo. The subject and/or caregiver will administer the second dose of AP-PA02 or placebo with clinic staff observation after the subject has been trained on proper administration. Clinic staff will confirm

the subject/caregiver is comfortable with administering AP-PA02 or placebo during this visit. If the subject is not comfortable administering AP-PA02 or placebo, the subject may visit the clinic for study drug administration until he/she or the caregiver is comfortable with proper study drug administration.

Subjects in Cohort A will receive study treatment (AP-PA02 or placebo) administered as 1 dose distributed over 2 administrations given 6 hours apart on the same day on Day 1 and 10-12 hours apart each day on the remaining days on 10 consecutive days, with 28 days of follow-up after the last study drug dose. Subjects in Cohort B will receive study treatment (AP-PA02 or placebo) administered as 1 dose distributed over 2 administrations given 6 hours apart on the same day on Day 1 and 10-12 hours apart each day on the remaining days for 10 consecutive days plus their current antipseudomonal inhaled antibiotic for 28 days (10 days of study drug treatment plus an additional 18 days). Subjects in Cohort B will also have 28 days of follow-up after the last study drug dose.

5.5.4 Treatment Compliance

Details of the date and time when the study drug is administered, along with any deviation from the procedure described in this Protocol, will be recorded in the subject's source documents and the eCRF for the days study drug is administered in the clinic. For the days subjects administer study drug at home, treatment compliance will be documented in a subject diary and will be assessed by the diary entries, including date, times, and whether the complete dose was administered, and returned study drug.

